## 7 STATISTICAL METHODS

### 7.1 Sample Size

Since the drug regulatory authority did not require specific population surveillance in this project, general population surveillance will be adopted. This study will not impose rigid rules on the sample size of specific populations. Sponsor will collect safety data as much as possible.

### 7.2 Analysis Population Definitions

- **Safety population:** Subjects who has signed an ICF and has at least partially taken the drug. It is the primary population for safety evaluation in post-marketing intensive monitoring.

### 7.3 Statistical Analysis

Analyses will be performed by sponsor or its representatives. Statistical methods will be primarily descriptive in nature. No formal statistical tests will be performed.

All statistical analyses will be presented overall.

#### 7.3.1 *Demographics and other Baseline Characteristics*

Demographic and baseline clinical characteristics analysis will be performed on the safety population. Descriptive summary statistics (number of available data, number of missing data, mean, standard deviation, median, minimum and maximum for continuous data, and frequency count and percentage for categorical data) will be calculated for demographic and baseline clinical characteristics (e.g. gender, age, weight, etc.).

Missing data will not be replaced but they will be displayed in all relevant tables.

#### 7.3.2 *Subject Disposition*

The following will be summarized:

- Subject signed ICF;
- Subject has at least partially taken the drug;
- Subject allocation by site.

#### 7.3.3 *Safety Evaluation*

AEs will be coded using the latest version of MedDRA and presented as “Preferred Terms (PT)

and System Organ Classification (SOC)".

Descriptive summary statistics of SAEs, AESIs and other nonserious AEs, related or unrelated to Compound Sodium Picosulfate Granules, will be presented. The main contents include the incidence, seriousness, of known ADRs/AEs and unexpected ADRs/AEs, as well as the occurrence of ADRs/AEs in specific populations. The covariates like age, gender and relevant risk factors (e.g. decreased renal function, non-compliance of drug administration or liquid intake, etc.) for the AE will be examined. Analyses and summary tables will be based upon the registry population.

Statistical analyses will present the overall results as well as separately for the specific populations.

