**METHODOLOGY**

This is a post-marketing multi-site, prospective, non-interventional study. Compound Sodium Picosulfate granules or other similar drugs will be prescribed to the subject based on physicians' clinical judgement.

The study will collect all stipulated events reported from signing the informed consent form (ICF) to about 37(+2) hours after first medication. Contacting the subject remotely by pharmacist or hospital staff will be used to collect adverse events/reactions and other relevant information. No additional tests or examinations will be performed on subjects, no drugs will be provided to the subjects.

- The study staff will register the eligible subjects. The subjects will sign the informed consent, provide contact information. Demographic characteristics (gender, age, nation, height, weight) of subjects will be collected.
- Contact the subjects remotely 37(+2) hours after first medication to collect any adverse events and information on the Compound Sodium Picosulfate granules administration.

All adverse events collected will be sent to the sponsor for case processing.

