## 5 STUDY PROCEDURES

The study procedure includes following steps:

1. Provide signed and dated written informed consent form prior to any procedure related to the study.
2. Evaluate subjects agreed to participate in study to make sure they meet inclusion and exclusion criteria.
3. Register eligible subjects and collect subject demographics and characteristics (gender, age, nation, height and body weight).
4. Follow up the eligible subjects 37 (+2) hours after the first medication.

For the subject who experienced AE, the following information will be collected to evaluate the safety profile of Compound Sodium Picosulfate Granules in real-world clinical practice.

- Medicinal information (administration time and dosage) and indication
- Concomitant medications
- Medical history
- Relevant lab test and its result: for the subject who experienced AE, collect relevant lab tests and its results subjects may receive as much as possible
- Safety evaluation

All stipulated events reported from signing the ICF to about 37(+2) hours after the first medication. AE information include the nature, the start date and end date, the relationship to the medicinal product, the seriousness, the outcome, and the use of corrective treatment, etc.

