### 6.3 Definition of Unexpected Adverse Drug Reactions

Unexpected adverse reaction refers to a drug reaction whose nature, severity, specificity, or outcome is not consistent with the term or description listed in the current local/regional label. This includes events that may be symptomatically and pathophysiological related to an event listed in the labelling but differ from the event because of greater severity or specificity. For example, under this definition, hepatic necrosis would be unexpected (by virtue of greater severity) if the labelling only referred to elevated hepatic enzymes or hepatitis. Similarly, cerebral thromboembolism and cerebral vasculitis would be unexpected (by virtue of greater specificity) if the labelling only listed cerebral vascular accidents.

"Unexpected," as used in this definition, refers to an adverse drug experience that has not been previously observed (i.e. not included in the label) rather than from the perspective of such experience not being anticipated from the pharmacological properties of the pharmaceutical product.

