## 6.5 Collection of Adverse Events

The study will collect all stipulated events reported from signing the ICF to about 37(+2) hours after the first medication. Sponsor will capture any adverse events collected during the subject's remotely contact by pharmacist or hospital staff.

Pharmacist or hospital staff will report any adverse events collected during the subject's remotely contact to Ferring (E-mail: PPD ) within the following timelines:

- 1) Fatal events, whether they are related/unrelated, must inform the sponsor immediately (within 24 hours of the knowledge of the event).
- 2) All other AE reports must be sent to the sponsor within 3 calendar days of knowledge of the event or receipt of significant follow-up information.

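### Section 7.3.3 rests the adverse-event tables on an undefined population, and with an open sample size the plan requires no measure of precision for its incidences

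*Combined protocol and SAP*

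**What the plan says.** **Output.** Section 2 makes the incidence of known adverse drug reactions (ADRs) and of serious events and reactions an objective, together with observing unexpected ones. Section 7.3.3 repeats this: "The main contents include the incidence, seriousness, of known ADRs/AEs and unexpected ADRs/AEs". Section 6.3 supplies the line between known and unexpected: an unexpected reaction is one "not consistent with the term or description listed in the current local/regional label".

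**Sample size and summaries.** The Synopsis (Number of Subjects) and section 7.1 set no target, minimum or maximum. The Synopsis (Statistical Methods) prescribes counts and percentages for categorical data and an incidence for each adverse event (AE). It and section 7.3 exclude formal testing. No section asks for a confidence interval, standard error or upper limit on an incidence.

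**Population.** Section 7.3.3 states: "Analyses and summary tables will be based upon the registry population". Section 7.2 defines only the safety population (consent plus at least partial intake) and says of it: "It is the primary population for safety evaluation in post-marketing intensive monitoring". Section 7.3.1 uses the safety population.

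**Collection.** Section 6.5: "The study will collect all stipulated events reported from signing the ICF to about 37(+2) hours after the first medication". According to the Synopsis (Methodology), the remote contact at 37(+2) hours is made "to collect any adverse events and information on the Compound Sodium Picosulfate granules administration". Section 5, however, lists administration time and dosage only among the items for subjects who had an AE. Section 3.3.2 accepts that follow-up may be lost. Section 7.3.2 counts subjects by consent, by intake and by site, but not by whether they were reached.

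**Tests.** Synopsis (Methodology): "No additional tests or examinations will be performed on subjects". Section 5 limits laboratory data in this way: "for the subject who experienced AE, collect relevant lab tests and its results subjects may receive as much as possible".

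**The concern.** An incidence needs a defined numerator, a defined denominator and some statement of how precise it is. Here the denominator named for the main safety tables has no definition, and nothing requires a statement of precision. Because the sample size is known only at the end, the same printed 0% could rest on a few hundred subjects or a few thousand.

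This matters most for zero or very few events. The label table in section 1.2.3 places anaphylactic reaction and convulsions in its uncommon band, which runs from 1/1000 to just under 1/100. A report with no such case would be read as reassuring, yet it need not say which part of that band the data exclude.

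The second exposure is the subject who is never reached. Both the AE report and the intake information come from the one contact. If such a subject stays in the denominator, absence of contact is counted as absence of events and every incidence is pulled down.

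**Working it through.** The plan states no sample size, precision or power, so there is no figure of its own to reproduce. Every N below is an assumption. The 3000 subjects in the version history were deleted from the plan; 3000 serves here only as one point in the range.

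**1. Zero or one event.** The exact two-sided 95% (Clopper-Pearson) upper limit after zero events is 1 − 0.025^(1/N). For one event it is the 97.5% quantile of a Beta(2, N − 1) distribution.

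| Assumed N | Upper limit, 0 events | Upper limit, 1 event |
|---|---|---|
| 300 | 1.22% | 1.84% |
| 500 | 0.74% | 1.11% |
| 1000 | 0.37% | 0.56% |
| 2000 | 0.18% | 0.28% |
| 3000 | 0.12% | 0.19% |

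Between N = 300 and N = 3000 the zero-event limit changes about tenfold (1.2221/0.1229 = 9.9). For it to reach 1/1000, N must be at least ln(0.025)/ln(0.999) = 3687.03, so 3,688. By the one-sided 95% convention the figure is ln(0.05)/ln(0.999) = 2994.23, so 2,995.

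**2. How often so few events would be seen.** P(0 or 1) = (1 − p)^N + Np(1 − p)^(N − 1).
- True rate 0.1%: 91% at N = 500, 74% at 1000, 20% at 3000.
- True rate 0.5%: 29% at N = 500, 4% at 1000.

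**3. What the interval can and cannot tell.** At N = 500, the intervals after zero events (up to 0.74%) and after one event (up to 1.11%) both contain 0.1% and 0.5%. At N = 1000, one event (0.003% to 0.56%) still contains both; only zero events (up to 0.37%) excludes 0.5%. At small N, then, the interval shows that the two rates cannot be told apart. That is the information the report need not give at present.

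**4. An observed 1%.** 5/500 gives 0.33% to 2.32%; 10/1000 gives 0.48% to 1.83%; 30/3000 gives 0.68% to 1.42%.

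**5. Subjects not reached (hypothetical shares, 1000 subjects).** The documents give no contact rate. If subjects not reached stay in N, 10 events read 10/1000 = 1.00% and the zero-event limit reads 0.37%. On those reached:

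| Reached | 10 events | Zero-event upper limit |
|---|---|---|
| 900 | 1.11% | 0.41% |
| 800 | 1.25% | 0.46% |
| 700 | 1.43% | 0.53% |

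**6. Population wording.** Sections 7.2 and 7.3.1 point to the safety population and 7.3.3 to the registry population. The conflict lies within the current text. The version history shows only what was probably intended, since it records the registry population as replaced. The numerical effect cannot be calculated, because the registry population has no current definition.

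**The case against.** The case on the other side has four parts.

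- **The study is descriptive and single-arm.** Once the denominator is named, any reader can derive exact limits from n and N, so no estimate changes. This stands in part: the missing interval is a reporting gap, not an error of analysis. But an interval is estimation, so the exclusion of formal tests does not answer the point. A reader can derive sound limits only if the report gives a denominator that is defined and whose contact status is known.
- **The population sentence is evidently leftover text.** This stands. The intent is clear and the correction is small, but the sentence still governs the main safety tables.
- **Section 7.2 already requires at least partial intake.** If intake is learned only at the contact, the intake count in 7.3.2 approximates the number reached. This is a reasonable reading, but the text does not secure it. Section 5 lists administration details only for subjects with an AE, section 3.2 requires only a prescription, and the second inclusion criterion could lead a site to presume intake from enrolment.
- **Section 7.3.1 says missing data will be shown and not replaced.** That sentence sits under demographics and does not say how a subject with no contact enters an AE table.

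A reader might also infer that the registry population is a wrong denominator that biases the results. The documents do not support that: without a definition, it cannot be shown to differ from the safety population in any given direction.

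**Conclusion.** The point holds, as something that should be corrected before the analysis. It does not invalidate the study. Two facts rest on the text alone: 7.3.3 names a population that is undefined and conflicts with 7.2 and 7.3.1, and no precision measure is required for the incidences that are the study's objective. The size of the precision gap rests on the assumed N: a zero count is compatible with anything up to 1.22% at 300 subjects and 0.12% at 3000. The effect of non-contact rests on hypothetical shares and cannot be estimated from the documents. They show only that subjects not reached could be counted as event-free, not that they will be.

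Three stronger readings are tempting and should be resisted.
- The open sample size is not itself an error. It is a stated choice; what is missing is a statement of what the achieved number supports.
- The plan does not forbid intervals; it merely fails to require them.
- An interval would not rescue every incidence. It covers sampling error only. It does not cover events that subjects fail to declare (section 3.3.1) or the expected bowel symptoms left unrecorded under 6.7.6. Nor does it cover abnormalities found only by tests, such as hyponatraemia, because no tests are added and laboratory results are sought only after an AE.

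**What to change.** 1. **Section 7.3.3, population.** Replace the registry population with the safety population as defined in 7.2.
2. **Section 7.3.3, precision.** Present subject-level incidence of any AE, serious AE, ADR, serious ADR and unexpected ADR, and of the preferred terms for known ADRs, as n/N, percentage and exact (Clopper-Pearson) two-sided 95% interval. Where the count is zero, give the upper limit at the achieved N for serious ADRs overall, unexpected ADRs overall and known symptomatic ADRs. State that the limit reflects sampling error only. Give no zero-event limit for reactions that only a test would reveal.
3. **Sections 7.2 and 7.3.2, subjects not reached.** Add the number reached at the 37(+2) hour contact to the disposition summary. Count a subject in the safety population only where at least partial intake is confirmed, and report subjects with unconfirmed intake separately. Repeat the main incidences on subjects reached, as a sensitivity analysis.

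Item 3 works only if intake is recorded for every subject contacted. Section 5 should therefore be aligned with the Synopsis on this; otherwise event-free subjects would drop out of the denominator and the incidences would be inflated.

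The cost is one extra column per incidence table, one disposition line, one repeated table and possibly one contact-status field. Statements about rare events become more modest. Enrolment does not change.

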#### **7.4      Interim Analyses**

No interim analyses are planned for this study.

## 8 DATA HANDLING

This study collect AEs, medications and other relevant information with remotely contacted by pharmacist and hospital staff. The subjects' data will be input into the database by the delegated staff. The subjects will be identified only by Study ID and subject number in the export database for analysis.

If the written informed consent of a subject is known not to be available in spite of it being required, data for this subject is not entered into or is deleted from the export database.

The safety data (AEs report) filed in AE form will be input into Ferring global safety database. The sponsor is responsible for processing AE/ADR in the safety database.

The coding of AE, medical history, concomitant medication, concomitant non-drug therapies and concomitant surgery terms will be performed. Concomitant medications will be coded using the World Health Organisation Drug Dictionary (WHODRUG) and AEs/medical and surgical history and nondrug therapy terms will be coded using the latest version of MedDRA.

On request, Pharmacist or hospital staff will provide the sponsor with additional data relating to the study, duly anonymised and protected in accordance with applicable requirements.

## **9      QUALITY CONTROL**

### **9.1     Monitoring**

Before the first subject is recruited into the study, sponsor will work with the investigational personnel to review and discuss the study protocol and related documents, as well as their responsibilities with regards to protocol compliance. Training will be conducted in accordance with the prescribed study procedures, and records of all participants will be kept.

Sponsor reserves the rights of monitoring the data to verify that they are accurate and complete and that the study is conducted in compliance with the protocol, GPP and regulatory requirements. Assigned monitors will conduct a combination of remote data reviews (with email and telephone contacts) and periodic local visits to address specific requirements and data quality. The monitor can access all original data, documents and records of the study and perform source data verification including verification of informed consent of participating subjects.

All the monitoring activities will be performed in accordance with sponsor SOP.

### **9.2     Audit/Inspection**

Similarly, audits/inspections may be conducted during the study and/or at the end of the study by representatives of the sponsor or external competent authorities. In this later case, the sponsor will be informed immediately. The auditor can review all medical records, study-related documents, and the ICF. The purpose of an audit is to ensure that ethical, regulatory and quality requirements are fulfilled in all studies performed by the sponsor.

## **10 CHANGES IN CONDUCT OF THE STUDY**

### **10.1 Protocol Amendments**

Any change to this protocol will be documented in a protocol amendment, issued by the sponsor. Amendments will be submitted for consideration to the approving central ethics committee (EC) and/or RA, as applicable. Approval is required for amendments which could affect the safety of the subjects, or which entails a change to the scope/design of the study.

### **10.2 Premature Termination of Study Sites**

The sponsor reserves the rights to terminate the participation of individual study sites. Conditions that may warrant termination include but are not limited to, insufficient adherence to protocol requirements and failure to enter subjects at an acceptable rate.

## 11 REPORTING AND PUBLICATION

### 11.1 Non-Interventional Study Report

The data and information collected during this study will be reported in a drug intensive monitoring study report prepared by the sponsor or its designee.

### 11.2 Confidentiality and Ownership of Study Data

Any information relating to the medicinal product or the study, including any data and results from the study is confidential information and will be the property of the sponsor. The investigational personnel will protect the confidentiality of this proprietary information belonging to the sponsor and not disclose such information unless in accordance with the drug intensive monitoring study agreement agreed between the sponsor and the implementing party.

### 11.3 Publication and Public Disclosure

#### 11.3.1 *Publication Policy*

The procedures for scientific result publication and authors involved in these publications and communications will be defined by the sponsor which reserves the worldwide copyright of all-important publications, including translations into other languages.

The sponsor reserves the rights to:

- Use the study results for any regulatory procedure, on its own behalf or that of subsidiaries.
- Present the results in its medical information letter on drugs.
- Distribute reprints of the publications.

No one may use these rights without the prior written authorization of the sponsor.

#### 11.3.2 *Public Disclosure Policy*

The sponsor will register non-interventional studies in an appropriate registry, i.e. [www.ClinicalTrials.gov](http://www.ClinicalTrials.gov), (a website maintained by the National Library of Medicine (NLM) at the U.S. National Institutes of Health (NIH)) and any local registries as required by local/national legislation.

## **12 ETHICAL AND REGULATORY ASPECTS**

### **12.1 Ethics Committee**

A central EC will review the protocol and amendments in accordance with applicable national requirements. The central EC will review the Subject Information and the ICF, their updates (if any), and any written materials given to the subjects.

### **12.2 Regulatory Authority(ies) Authorisation / Approval / Notification**

The permission to perform the study will be obtained in accordance with applicable national regulatory requirements. All ethical and or regulatory approvals in accordance with national legislation must be available before the study is initiated.

### **12.3 Subject Information and Consent**

Prior to any procedure related to the study, informed consent must be obtained from subjects. Informed consent can be expressed verbally or in writing, an official ICF must be dated and signed personally by the subject (or witness/legal representative, if applicable).

The investigational personnel will explain the nature, purpose, possible risk and benefit of the study to each subject (or witness/legal representative, if applicable). The subject must be given ample time to consider participation in the study, before the consent is obtained. Each subject will be informed that he/she is completely free to refuse to enter the study or to withdraw from it at any time, without any consequences for his/her further care and without the need to justify their decision. In case the subject decides to withdraw from the study, the data collected up to this point will be used.

Concerning the study data, the subject will accept by signing the ICF that their medical records may be viewed by the sponsor, RA, a mandated auditor and/or the study monitor in compliance with the statement of confidentiality.

